11.3 Measures of Primary and Secondary Outcomes

11.3.1 Timeline Follow-back (TLFB)

The Timeline Follow-back procedure²¹ will be used to elicit the participant's self-reported use of substances at baseline and throughout study participation. At screening, this form will be used to assess substance use for the 30-day period prior to admission to the inpatient treatment program. At Week 1, the TLFB will assess the period from discharge to the community up to the date preceding the Week 1 visit (the time in detox and/or short-term residential is not captured on this assessment). At weeks 4 and 8, the TLFB will assess each day since the previous TLFB assessment.

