### **1.5 Randomization**

There is no randomization in this study.

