### **2.3 Treatment Plans**

To evaluate the outcomes, two main sub-groups from the observational cohort are (1) participants who receive any medication-assisted treatment (MAT) and (2) participants who do not receive medication-assisted treatment. Assessment of the participant's intention for treatment after discharge to community (i.e., leaving the detox and/or short-term residential unit) was assessed at the Day 0 visit (Community Discharge Plan). On the Medical Management (MM) Community Treatment form, at weeks 1, 4 and 8, participants were asked what treatment(s) he/she was engaged in, with the options being

- (1) MAT with buprenorphine maintenance
- (2) MAT with injectable naltrexone
- (3) MAT with oral naltrexone
- (4) MAT with methadone maintenance
- (5) MAT with inpatient detox
- (6) Psychosocial
- (7) Referral to other community-based treatment
- (8) Declined further treatment.

A participant will be categorized as having received any medication-assisted treatment post-discharge if at any visit (Weeks 1, 4, and 8), the treatment plan engaged in includes medication-assisted treatment.

Program type and high severity vs. low severity at baseline will also define groups to be separately analyzed. The program type subgroups will be defined based on the length of stay in the detox and/or residential facility. The date of admission to the detox unit is found on the Detoxification Utilization Summary form and the corresponding dates of discharge for both the detox unit and residential facility are found on the enrollment form. If the subject was discharged to the community from the residential facility, the total time in detox and the residential facility will be calculated. The difference between admission and discharge dates will be tabulated and categorized based on the following groupings: (1)  $\leq 7$  days, (2) 8-20 days and (3)  $\geq 21$  days.

High severity and low severity opioid use level at baseline will be defined as computed for the main CTN-0051 study stratification factor (i.e.  $< 6$  bags vs.  $\geq 6$  bags). To compute the opioid severity level, if the primary opioid of use in the last 7 days was not heroin or the route of administration is not IV-injection then that participant is defined as a low severity user. For IV heroin users where the quantity is not provided in bags but in dollars, bags are estimated as the dollar amount/10 rounded to the nearest integer.

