#### 3.2 Sample Size and Power Calculations

##### 3.2.1 Rationale for Sample Size and Statistical Power

No formal statistical hypothesis tests will be calculated for this study; therefore, there is neither sample size nor statistical power calculations. The study population is a convenience sample and it is anticipated that each participating site should be able to enroll approximately 60 participants for a total of approximately 360 participants. While the main objectives of this study are descriptive in nature, such as estimating the opioid use rate eight weeks after discharge to the community, it may be of interest to evaluate whether these opioid use outcomes are associated with certain covariates. Potential independent predictors of opioid use include: age, gender, race, ethnicity, use of medication-assisted treatment, and type of treatment received prior to discharge to the community.

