### **5.5 Analysis Methods**

For modeling the days to first opioid use and days to regular opioid use outcomes measures, a Cox regression model will be used after an assessment of the proportional hazards assumption. Should the key proportional hazards assumption be violated for a particular outcome and covariate, alternative models will be considered. The second set of outcomes relate to the number of days of opioid use. It is anticipated that the number of days of use will be non-normal, however we elect to analyze the data via a *t*-test which is fairly robust to misspecification of the underlying outcome distribution. Quantile regression may be used if modeling with multiple covariates is appropriate. For UDS-based outcomes, the dependent variable is binary (i.e., indicator of use or indicator of missingness) so univariate comparisons will be made using Pearson's  $\chi^2$  and any multivariate modeling will be implemented using logistic regression.

The second set of outcomes relate to the number of days of opioid use. It is anticipated that the number of days of use will be non-normal, however we elect to analyze the data via a *t*-test which is fairly robust to misspecification of the underlying outcome distribution. Quantile regression may be used if modeling with multiple covariates is appropriate. For UDS-based outcomes, the dependent variable is binary (i.e., indicator of use or indicator of missingness) so univariate comparisons will be made using Pearson's  $\chi^2$  and any multivariate modeling will be implemented using logistic regression.

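### The exploratory MAT versus No-MAT contrast has no prespecified adjustment for baseline severity or pre-admission opioid use, so it may partly reflect case-mix

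*SAP*

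**What the plan says.** SAP 1.5 states "There is no randomization in this study". Under SAP 2.3, a participant counts as MAT if the treatment reported at any of Weeks 1, 4 or 8 includes it. The same section makes MAT and No MAT the two main subgroups.

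SAP 5.5 sets the comparisons:

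- **Days of use:** "It is anticipated that the number of days of use will be non-normal, however we elect to analyze the data via a" t-test. Quantile regression is permitted if several covariates are wanted.
- **UDS:** "univariate comparisons will be made using Pearson's" chi-square, and "any multivariate modeling will be implemented using logistic regression".
- **First and regular use:** Cox regression, subject to a check of proportional hazards, with no covariates named.

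The only list of candidate covariates is in the sample-size rationale (SAP 3.2.1, repeated from Protocol 13.2): "Potential independent predictors of opioid use include: age, gender, race, ethnicity, use of medication-assisted treatment", plus the type of treatment received before discharge.

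Two further baseline measures exist. On severity, SAP 2.3 says: "High severity and low severity opioid use level at baseline will be defined as computed for the main CTN-0051 study stratification factor". On pre-admission use, Protocol 11.3.1 says of the Timeline Follow-back (TLFB) at screening that "this form will be used to assess substance use for the 30-day period prior to admission". Neither is on the list.

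**The concern.** Whoever enters MAT after discharge may differ beforehand from whoever does not. Severity of use and recent use are plausible common causes of MAT entry and of later opioid use. If they differ between the groups, a crude difference in use days or UDS positivity mixes that difference with anything associated with MAT.

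The bias could run either way. If heavier users more often enter MAT, a benefit could be hidden. If they less often do, one could be created.

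The SAP comes close to addressing this. It adds severity as a subgroup, which Protocol 13.3 did not have, and crosses it with MAT in Table 5. But Table 5 holds counts only, and Tables 10, 13, 16 and 19 split outcomes by severity alone. Nothing specified brings severity into the MAT contrast. If covariates are chosen after the data are seen, the choice is open to the results.

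**Working it through.** **1. The plan's own figures, which contain no covariate**

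- *UDS* (SAP 3.2.4, Table 3: N = 360, half in each group, 50% event rate, OR 1.85, stated power 82%). The second proportion is 1.85/2.85 = 0.649. With 180 per group, the pooled standard error is 0.0521 and the unpooled one 0.0515. z = (0.149 − 1.96 × 0.0521)/0.0515 = 0.91, so power is 81.9%. This reproduces.
- *Days of use* (SAP 3.2.4, Table 2: N = 360, SD 4.5 in both groups, difference 1.5, stated power 88%). SE = 4.5 × √(2/180) = 0.474, and 1.5/0.474 − 1.96 = 1.20, so power is 88.5%. This reproduces.

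Both are crude two-group calculations, matching the comparisons SAP 5.5 commits to.

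**2. What case-mix alone could produce**

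The documents give neither the severity mix by MAT nor the effect of severity on outcome. All inputs in this step are assumptions, with the MAT effect set to zero.

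*Days of use.* Spurious difference = (difference in high-severity prevalence) × (severity effect in days):

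| Imbalance | 5-day effect | 10-day effect |
|---|---|---|
| 10 points | 0.5 | 1.0 |
| 20 points | 1.0 | 2.0 |
| 30 points | 1.5 | 3.0 |

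A difference of 1.5 days appears in five of the six rows of Table 2. With 180 per group, a spurious 1.5 days is declared significant 88% of the time at Table 2's SD of 4.5, but 16% of the time if the SD is 15 (also an assumption).

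*UDS.* N = 360 split equally, 50% positive in the MAT group. Worked case: severity OR 3, high severity 40% in MAT and 60% in No MAT. Positivity must be 39.3% in low-severity and 66.0% in high-severity participants, since 0.4 × 0.660 + 0.6 × 0.393 = 0.50. No-MAT positivity is then 0.6 × 0.660 + 0.4 × 0.393 = 0.553. The crude OR is 0.553/0.447 = 1.24, and chi-square rejects 17% of the time against a nominal 5%. The range:

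| High severity, MAT / No MAT | Crude OR (severity OR 2 / 3 / 4) | Rejection (severity OR 2 / 3 / 4) |
|---|---|---|
| 45% / 55% | 1.07 / 1.11 / 1.14 | 6% / 8% / 10% |
| 40% / 60% | 1.15 / 1.24 / 1.31 | 10% / 17% / 24% |
| 30% / 70% | 1.32 / 1.54 / 1.71 | 25% / 52% / 71% |

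**3. What adjustment for severity costs**

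With equal groups, the squared correlation between MAT and severity is 0.2² = 0.04 for the 40/60 mix and 0.4² = 0.16 for 30/70. The unadjusted z of 1.96 + 0.91 = 2.87 is multiplied by √(1 − R²):

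- 40/60: 2.87 × √0.96 − 1.96 = 0.85, power about 80%.
- 30/70: 2.87 × √0.84 − 1.96 = 0.67, power about 75%.

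Both compare with 81.9% unadjusted. The loss is largest where the imbalance, and so the need to adjust, is largest.

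**The case against.** The strongest reply is that the study makes no causal claim about MAT. Its objective is to estimate treatment-as-usual rates. Protocol 13.4 and SAP 5.5.1 call the primary objectives descriptive and rule out formal testing. Crude rates within each subgroup are then the stated target. This stands. A reader might infer that Tables 8, 11, 14 and 17 credit a severity difference to MAT. They do not: they hold counts and summary statistics, with no p-value or effect estimate. The issue is confined to the exploratory comparisons. Those are planned, since SAP 5.5.1 promises comparisons through modelling and SAP 3.3 sets a two-sided 5% level for all tests. The caution in SAP 3.3 concerns multiplicity, not confounding.

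A reader might also infer that the plan rules out adjustment or closes the covariate list. It does neither. Cox, logistic and quantile models are named, and the list is worded as potential and inclusive. What is missing is commitment and content: the adjusted models for days of use and UDS are optional, no model has a stated covariate set, and the one list omits both variables.

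Three limits on the remedy also stand:

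- The severity variable is coarse: anyone not injecting heroin intravenously is classed as low severity.
- Pre-admission use days may lie near their ceiling. One cited US detoxification cohort averaged 28 days of heroin use in the month before admission (Protocol 4.1). Adjustment may then remove little.
- MAT status is read from reports during follow-up, which overlaps the outcome period. No baseline covariate repairs that.

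**Conclusion.** The point holds as a low-cost improvement to exploratory analyses. The groups are not randomised, the committed comparisons for days of use and UDS are unadjusted, and two relevant baseline variables already collected are left out of every specified MAT comparison. Table 5 would show a severity imbalance, but no planned analysis acts on it.

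The size is unknown. The 1.5-day figure needs both a 30-point imbalance and a 5-day severity effect, and neither is anchored in the documents. With a 10-point imbalance, UDS rejection is only 6% to 10%. The documents do not support a claim that the MAT contrast is biased by a given amount or in a given direction. Nor do they support making an adjusted estimate the headline result or reading it causally: the contrast is exploratory, and adjustment for two variables leaves residual confounding.

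**What to change.** In SAP 5.5, for the exploratory MAT versus No-MAT contrast, prespecify adjusted models that include baseline severity (high/low) and opioid-use days from the 30-day pre-admission TLFB:

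- Cox regression for days to first use and days to regular use;
- logistic regression for UDS;
- one named regression for days of use. A linear model keeps the mean difference that the t-test and Table 2 use; quantile regression would change the target. The SAP should choose one.

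Add both variables to the list in SAP 3.2.1. Keep the crude tables and tests, and report the adjusted estimates with confidence intervals beside them. Label them as associations. State that adjustment does not remove residual confounding, nor the problem that MAT status is defined from reports during follow-up.

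The cost is SAP wording and a few model statements, with no new data. There is a small loss of power (step 3 of the working). A rule is needed for participants whose severity or screening TLFB is missing, either a missing category or exclusion from the adjusted model with the number stated.

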#### **5.5.1 Statistical Significance**

There are no hypotheses being evaluated in this observational study with solely descriptive primary objectives, thus no formal statistical testing will be conducted. Exploratory comparisons will be made via modeling as described in Section 5.5.

#### **5.5.2 Minority/Gender Analyses**

In accordance with NIH guidelines, analyses will be completed to determine whether the outcomes of interest were significantly affected by participant minority/gender status.

## **6.0 MISSING DATA**

The number of missing as well as the number of positive and negative UDSs will be tabulated separately when calculating the UDS outcome at baseline, and weeks 1, 4 and 8. Analyses of self-reported use time to event outcomes (e.g. time to first use) will impute intermittent missing days as use, but will not impute missing days due to drop-out or loss-to-follow-up. When tallying the days of opioid use, all missing self-reported days will be imputed as positive. The number of days imputed for each subject will also be summarized.

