3.0 STUDY SCHEMA

4.0 INTRODUCTION

4.1 Background and Significance to the Field

For opioid use disorder patients in the U.S. and most of the rest of the world, detoxification or detoxification followed by short-term residential treatment, with the goal of achieving long-term abstinence from opioid misuse is a mainstay of treatment. Although it is widely believed that many patients treated in this way will rapidly relapse to opioid misuse – leading to a costly and ineffectual cycle of readmission for repeated detoxifications – there is scant data on opioid use outcomes following discharge from these programs. Searches of PubMed, NIH Reporter, and ClinicalTrials.gov for “clinical outcomes following opioid detoxification” and the like, mostly

reveal studies focused on detoxification methods, medication schedules, withdrawal symptomatology, tolerability and the proportion of patients completing detoxification.¹⁻⁶ Three studies,⁷⁻⁹ two of them from Europe, focused on subsequent outcomes (e.g., use, misuse, relapse) after patients completed detoxification. Gossop et al⁷ followed eighty patients discharged from 21-day methadone withdrawal programs at two United Kingdom hospitals between 1984 and 1986. Seventy-one percent used opioids within the first six weeks of discharge, and 81% used opioids at some point during the six-month follow-up, though at the six-month endpoint 51% were opioid-free. Broers et al⁸ followed 73 patients discharged from a Geneva, Switzerland 15-day (average) methadone tapering program between 1994 and 1995. Sixty-five percent were using drugs again (half of them regularly) within the first four weeks. At the six-month endpoint half of the population was physically dependent again. Chutuape et al⁹ followed 113 patients discharged from a 3-day medical (mostly clonidine) detoxification program in Baltimore, Maryland between May and November 1996. At the one-, three- and six-month post-discharge assessments, 25-36% reported almost daily use, 21-30% reported no use, and the remainder reported occasional use. Overall, the mean number of days of heroin use decreased from 28 days (in the month prior to admission) to 11-14 days. In addition, several studies, most of them randomized trials of buprenorphine detoxification, collected limited datasets on post-detoxification outcomes which were disappointing (only 3-47% self-reporting abstinence, and only 7-31% producing negative urine drug screens over one- to three-month follow up periods).¹⁰⁻²⁰

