13.5 Missing Data and Dropouts

The number of missing as well as the number of positive and negative UDSs will be tabulated separately when calculating the UDS outcome at weeks 1, 4 and 8. Analyses of self-reported use will impute intermittent missing days as use, but will not impute missing days due to dropout or loss-to-follow-up.

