## **2.0 OUTCOMES AND SUBGROUPS OF INTEREST**

The outcomes are (1) days to first opioid use and days to regular use, (2) number of days of use during the first four and eight weeks post-discharge to the community, and (3) number of positive, negative, and missing UDSs at weeks 1, 4, and 8. The number of participants abstinent for four weeks and those participants who were not will also be calculated.

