##### 3.2.4 Detectable Effect Sizes

Table 1 summarizes detectable effect sizes for the two outcomes: (a) time to first opioid use, and (b) time to first regular opioid use. The detectable hazard ratios (HRs) are calculated for various values of the standard deviation of the outcome measure and the overall percent of participants who had (a) used opioids or (b) regularly used opioids during the eight week follow-up period. Total sample sizes of 280, 320 and 360 were considered. If the target sample size of 360 is reached, and 60-70% of participants use or regularly use opioids by the week 8 follow-up visit, then there will be at least 80% power to detect a HR of approximately 1.46 with a type I error rate of 5%. On the other hand if only 320 participants are enrolled, then the detectable HR is around 1.50 and for 280 participants, then the detectable HR is around 1.40-1.75.

**Table 1.** Detectable hazard ratios for the outcomes measures time to (a) first opioid use, and (b) first regular opioid use

Total Sample Size	Detectable Hazard Ratio	Power (%)	Proportion of Participants who Used Opioids/ Regularly Used (%)	Standard Deviation of the Number of Days to First Opioid Use/Regular Use
280	1.75	83%	60%	0.4
	1.40	82%	70%	0.5
320	1.50	81%	60%	0.5
	1.47	83%	70%	0.5
360	1.47	82%	60%	0.5
	1.45	84%	70%	0.5

Table 2 summarizes detectable effect sizes for the outcomes based on the number of days of opioid use during the eight weeks post-discharge to the community of the study. The detectable mean differences for the two-sample *t*-test are calculated for various values of the group-specific mean and standard deviations of the outcome measure. Total sample sizes of 280, 320 and 360 were considered. If participants in one group use opioids on average two weeks out of the month, then we can detect a difference of 1.5 use days with at least 80% power (assuming a type I error rate of 5%) if the target sample size of 360 is achieved. Similarly, if participants in one group use approximately three weeks out of a month, then we can detect a difference of 1.5 days. With 320 participants enrolled, a mean difference of 1.5 days can still be detected with at least 80% power, but the detectable difference increases to 2.8 days with a total sample size of 280.

Table 2. Detectable differences in means for the number of days of opioid use during the eight weeks of follow-up				

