**Table 17: Summary of Days of Opioid Use by Type of Treatment Received Post-Discharge**

	Treatment Type Received Post-Discharge		
	Medication-assisted Treatment	No Medication-assisted Treatment	Total
Number of Participants			
Days of Opioid Use  up to Week 1			
N			
Mean			
SD			
Median			
Min			
Max			
Subjects Abstinent up to Week 1 N(%)			
Number of Imputed Days Per Subject (up to Week 1)			
N			
Mean			
SD			
Median			
Min			
Max			
Days of Opioid Use  up to Week 4			
N			
Mean			
SD			
Median			
Min			
Max			
Subjects Abstinent up to Week 4 N(%)			
Number of Imputed Days Per Subject (up to Week 4)			
N			
Mean			
SD			
Median			
Min			
Max			

 All missing self-reported use is imputed as positive.

 All missing self-reported use is imputed as positive.

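### The SAP scores every missing self-reported day as use in the days-of-use tally, against the protocol's rule, so for missing days the tally is an upper bound that rises with attrition

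*SAP*

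**What the plan says.** Protocol 13.5 has a single rule for the Timeline Follow-Back (TLFB) data: "Analyses of self-reported use will impute intermittent missing days as use, but will not impute missing days due to dropout or loss-to-follow-up". Days of use is a TLFB outcome (Protocol 9.1 and 13.1.1), so the rule covers it.

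SAP 6.0 splits that rule in two. Time-to-event analyses "will impute intermittent missing days as use, but will not impute missing days due to drop-out or loss-to-follow-up". For the count of use days the SAP says: "When tallying the days of opioid use, all missing self-reported days will be imputed as positive". Tables 17 to 19 repeat this in the footnotes to the Week 1, Week 4 and Week 8 tallies: "All missing self-reported use is imputed as positive".

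SAP 6.0 adds one disclosure: "The number of days imputed for each subject will also be summarized". Tables 17 to 19 carry matching rows by window and subgroup. The SAP gives no reason for departing from the protocol and no days-of-use table under the protocol rule.

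**The concern.** Days of use over the first four and eight weeks is a named outcome, to be estimated overall and by subgroup as part of the descriptive primary objective (Protocol 13.3; SAP 2.0, 2.3 and 5.0). Giving each missing day its highest possible value makes the reported mean a mixture of opioid use and loss to follow-up.

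The two rules differ where most missing days should lie. At Weeks 4 and 8 the TLFB reaches back to the previous TLFB (SAP 2.1), so a participant who misses a visit and then returns should leave few gaps. What remains missing should be mainly time after dropout, which the protocol leaves unimputed.

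The SAP is also inconsistent across its own outputs. A participant lost after Week 1 with no use reported would be censored without use in Figures 2 to 7, yet would carry 49 imputed use days (56 − 7) in the eight-week rows of Tables 17 to 19.

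**Working it through.** **The plan's own benchmark.** Table 2 (SAP 3.2.4) gives 82% power at N = 360 for 14.0 (SD 3.5) against 15.5 (SD 6.0). Common SD = √((3.5² + 6.0²)/2) = 4.91; SE = 4.91 × √(2/180) = 0.518; 1.5/0.518 − 1.96 = 0.94; power is 82.6% (82.4% with the noncentral t). The figure reproduces, so 1.5 days is a fair yardstick for this outcome.

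**Inputs.**
- Follow-up is 56 days (eight weeks, Protocol 6.2).
- q = share of participants lost. Neither document gives it; 20% is assumed, with 10% and 30% as a range where shown.
- d = last day with data; day 7 (after Week 1) or day 28 (after Week 4).
- r = share of days with use after leaving. The documents do not give this for dropouts. Their planning figures run from 14/56 = 0.25 (Table 2 mean of 14 under its eight-week caption), through 0.5 ("If participants in one group use opioids on average two weeks out of the month"), to about 0.75 (three weeks in a month, same paragraph).

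The Baltimore cohort in Protocol 4.1, where "the mean number of days of heroin use decreased from 28 days (in the month prior to admission) to 11-14 days", gives about 11/30 = 0.37 to 14/30 = 0.47. That lies inside the range, but it counts heroin only and averages a whole cohort, so it does not narrow r for people who have left.

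**Inflation of the mean.** Each lost participant gains (56 − d) imputed days, of which a share (1 − r) were not use days. Inflation = q × (56 − d) × (1 − r).

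| q = 20% | r = 0.25 | r = 0.5 | r = 0.75 |
|---|---|---|---|
| Eight weeks, loss after day 7: 9.8 × (1 − r) | 7.35 | 4.9 | 2.45 |
| Eight weeks, loss after day 28: 5.6 × (1 − r) | 4.2 | 2.8 | 1.4 |
| Four weeks, loss after day 7: 0.2 × 21 × (1 − r) | 3.15 | 2.1 | 1.05 |

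**Distance between the tally and a plain sum of reported use days.** This needs no r: q × (56 − d). At 10/20/30% loss it is 4.9/9.8/14.7 days after day 7 and 2.8/5.6/8.4 days after day 28.

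**Attrition gap that alone produces 1.5 days between subgroups with identical use.** Gap = 1.5/((56 − d)(1 − r)).
- Day 7: 1.5/36.75 = 4.1 points (r = 0.25); 1.5/24.5 = 6.1 (r = 0.5); 1.5/12.25 = 12.2 (r = 0.75).
- Day 28: 1.5/21 = 7.1; 1.5/14 = 10.7; 1.5/7 = 21.4.

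**Is another single figure better?** Take 20% lost after day 7, use on 25% of days while observed and 75% after leaving.
- True mean: 0.8 × 14 + 0.2 × (1.75 + 36.75) = 18.9.
- SAP tally: 11.2 + 0.2 × (1.75 + 49) = 21.35.
- Sum of reported days: 11.2 + 0.2 × 1.75 = 11.55.
- Use days over assessed days, scaled to 56: 11.55/46.2 × 56 = 14.0.

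Here the tally is closest. If dropouts instead use at 0.25, the truth is 14.0; the ratio is exact and the tally is still 21.35.

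**The case against.** Missing-as-use is a familiar cautious convention. The protocol rule does not say how to count days for someone who leaves, so the SAP is partly filling a gap. The imputation is footnoted, and the imputed days are tabulated by window and subgroup. Mean tally minus mean imputed days returns mean reported use days (21.35 − 9.8 = 11.55 in the example), which is a lower bound for missing days. Comparisons are exploratory (SAP 5.5.1). Time-to-event outcomes keep the protocol rule, and missing urine screens are tabulated separately.

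Much of this stands. A reader might infer that the imputation is hidden; the footnotes and imputed-days rows show that it is not. A reader might also infer that an attrition gap of 4 to 6 points is generally enough to create the 1.5-day difference. That holds only for loss after day 7 with r no higher than 0.5, and the planning text itself reaches about 0.75.

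What the disclosure does not provide is a split between intermittent and dropout days, medians or tests free of the imputed days, or any result under the protocol rule. The convention is also not cautious when subgroups are compared, because unequal attrition can move the difference either way.

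**Conclusion.** The point holds and should be fixed. The conflict between SAP 6.0 and Protocol 13.5 is in the text, and for missing days the tally is an upper bound by construction. It does not bound under-reporting on days that were assessed.

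The size is illustrative because it rests on assumed attrition. At 20% loss the eight-week inflation is 2.45 to 7.35 days (loss after day 7) or 1.4 to 4.2 days (after day 28) for r from 0.75 down to 0.25. An attrition gap of about 4 to 12 points (day 7) or 7 to 21 points (day 28) would by itself match the 1.5-day difference of Table 2.

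Three stronger readings are not supported. First, the documents do not show that the tally is further from the truth than the alternatives; if dropouts use heavily, it may be nearer. Second, they do not establish bias in the comparison by medication-assisted treatment, because SAP 2.3 does not say how participants with no follow-up visit are classified. Third, they do not show that abstinence is understated. SAP 2.0 says "The number of participants abstinent for four weeks and those participants who were not will also be calculated", but not whether imputed days count against it. The last two are separate clarifications and carry no weight in this conclusion.

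**What to change.** - Reconcile SAP 6.0 with Protocol 13.5, and state the reason for any departure.
- Label the all-missing-as-use tally in Tables 17 to 19 as an upper bound for missing days.
- Beside it, report an analysis under the protocol rule, imputing only intermittent gaps, with the number of days assessed. The protocol leaves the form of the count open, so the SAP must define it. One option is total use days over total assessed days, with a statement that this assumes dropouts use like those observed. Neither figure should stand alone.
- Split the imputed-days row into intermittent days and days after the last TLFB.

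The cost is SAP wording and a few table rows, with no new data. The downside is small: two figures to interpret instead of one, and a denominator that varies between participants and windows.
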